## Funder

The research is funded by Medical Physics & Clinical Engineering, RLBUHT.

## STUDY SUMMARY

This protocol describes the **EMu Pilot Study** and provides information about procedures for entering participants. Every care was taken in its drafting, but corrections or amendments may be necessary. These will be circulated to investigators in the Study. Problems relating to this Study should be referred, in the first instance, to the Chief Investigator.

This study will adhere to the principles outlined in the NHS Research Governance Framework for Health and Social Care (2nd edition) and Good Scientific Practice (Version 1). It will be conducted in compliance with the protocol, the Data Protection Act and other regulatory requirements as appropriate.

## GLOSSARY OF ABBREVIATIONS

HRA	Health Research Authority
REC	Research Ethics Committee
EMG	Electromyogram
EOM	Extraocular muscle
BTX	Botulinum toxin

## KEYWORDS

Extraocular muscle, electromyogram, monopolar, needle guidance, Botulinum toxin, strabismus

## TITLE

A data collection and analysis pilot study to indicate preliminary characterisation of the electromyogram signal in relation to needle position with respect to the extraocular muscles, as observed during electromyogram needle guided treatment of strabismus in adults

## DESIGN

A cross-sectional observational pilot study

## AIMS

Gain more knowledge of the electromyogram acquired during electromyogram (EMG) needle guided treatment of strabismus, indicate the feasibility of improving the technology and inform a larger study to provide evidence to underpin the development of such new technology.

## OUTCOME MEASURES

Primary

- The change in the EMG signal as the needle approaches, and enters, the target extraocular muscle.

## Secondary

- Clinician's score of the step change from baseline EMG to 'active' EMG level heard immediately prior to delivery of Botulinum toxin (BTX);
- Clinician's score of their confidence in accurate needle placement;
- Clinician's score of overall quality of the EMG signal heard during the procedure;
- Change in patient's angle of deviation following treatment.

## POPULATION ELIGIBILITY

Adults undergoing planned, routine EMG needle guided BTX injection into either lateral or medial rectus muscle for the treatment of strabismus.

## DURATION

Up to 20 weeks.

# 1 INTRODUCTION

## 1.1 BACKGROUND

### 1.1.1 Strabismus, Botulinum toxin and EMG

Strabismus is an ocular condition caused by unbalanced contraction of EOMs, specifically the medial or lateral rectus muscle. There are several functional consequences of the condition, and significant negative psychosocial effects that reduce quality of life (Durnian et al., 2011). In some cases, strabismus is treated with injections of BTX to temporarily inhibit the medial or lateral rectus muscle responsible for the excessive deviation of the globe, thus straightening the gaze.

The EOMs are histologically unique, being the only muscles in humans containing both slow fibres *and* fast-twitch fibres. Consequently, the motor unit potentials generated by EOMs are also unique, being of much lower amplitude and duration, and with a higher firing rate when compared to peripheral skeletal muscles (Björk, 1952).

Due to the deep location of the rectus muscles, the needle used to deliver BTX cannot be easily guided without assistance. The unique electrical activity of the EOMs described above is harnessed in combination with EMG needle guidance to help ensure the toxin is delivered correctly.

### 1.1.2 Current practice

An early publication described the application of EMG needle guidance in treating strabismus with BTX, whereby a needle electrode was used to pick up the EMG activity at the injection site, and by amplifying and playing the EMG signal through a loudspeaker, the clinician could learn to identify the correct location from the sounds. In this paper, Scott (1981) states “one learns to differentiate the low amplitude distant signal from the high amplitude and crackling sound when the centre of the muscle is reached”. The sound is also described as “rain on a tin roof” (Childers, 2003), and the increase in EMG volume together with the change in sound are discerned by the clinician as the patient gazes in the direction of the dystonic muscle into which the BTX is injected, thus activating the muscle.

Practice commonly observed today has not changed in the intervening 37 years. Today, as then, the sound is provided by a simple device that amplifies the EMG signal at the tip of the needle through which the BTX will pass when it is injected, and plays it through a loudspeaker. Devices today may also provide an indication of the signal level and/or the waveform morphology.

### 1.1.3 Existing research

There is very little research exploring the technology described above, and how it may be improved in the context of strabismus. Techniques with potential for improving EMG guidance include:

- *Visualisation of the waveform.* Kim et al. (2011) published a method of displaying the EMG

waveform to the clinician during delivery of BTX to treat strabismus. Kim et al. suggest displaying the waveform delivers an increase in accuracy and decrease in procedure time, although do not detail how this was achieved or measured.

- *Motor unit potential rise time.* Ajax et al. (1998) used a threshold applied to the motor unit potential rise time to determine correct positioning within limb muscles. They showed an improvement in localisation of the needle under EMG guidance compared to anatomic localisation.
- *High-pass filtering to remove noise.* Brown et al. (2010) performed experiments with rotator cuff muscles, and related signals from needle electrodes to signals from surface electrodes. They found that there was still good correlation between the two signals even when low frequency components of the surface signal below 240 Hz were removed. If, by extension, this applies to EOMs that contain even higher frequency components, then high-pass filtering may reduce interference without degrading the information from the target muscle.
- *Measuring parameters of the EMG spectrum.* Early research by Trimble et al. (1973) characterised the spectrum of an averaged extraocular motor unit potential, and found a peak around 900 Hz, in contrast to a high prevalence of much lower frequencies in skeletal muscles. Despite this evidence, Hunter et al. (1996), in a study of only 23 patients, did not find correlation between effectiveness of strabismus treatment and three basic parameters of the spectrum: tallest peak, peak frequency and total power. This may be due to the different electrode types used – Trimble et al. used coaxial electrodes capable of detecting more localised EMG than the monopolar electrode used by Hunter et al. However, recent unpublished evidence gathered at Medical Physics and Clinical Engineering, Royal Liverpool Hospital, using thread electrodes does suggest high frequency components of the EMG signal relate to EOM activity.
- *Interference analysis.* Werdelin et al. (2011) used bipolar electrodes with previously reported turn amplitude analysis (TAA) to guide BTX injections for the treatment of torticollis. The injection was performed subsequently to the analysis, suggesting TAA may not be achievable in the case of monopolar needle EMG.
- *Signal decomposition.* Decomposition of the EMG signal may allow single motor unit activity to be detected and characterised. Although reported using concentric (bipolar) needle electrodes (Pham et al., 2014), this technique may be useful in the analysis of monopolar EMG signals.

The publications above indicate possible improvements to the technology; however, the evidence is sparse and inconclusive in the context of EMG needle guided treatment of strabismus.

Specifically, while the EMG of individual motor units is well characterised, when monopolar needles of the type used in EMG guided BTX injections are used, the EMG signal represents the contribution of many motor units, and is not so readily interpreted.

## 1.2 RATIONALE FOR CURRENT STUDY

The rather imprecise “rain on a tin roof” identification of the EMG signal described above for what is a precise procedure – the medial and lateral rectus muscles are around 2.5 mm to 4.7 mm in diameter – will arguably negatively impact on treatment efficacy and repeatability. There may also be an increase in the likelihood of side effects such as ptosis and vertical deviation when the toxin spreads beyond the target muscle. When the needle is guided with direct observation into the muscle belly, the number of cases of ptosis is as low as 1 in 32 cases (Wan et al., 2011), suggesting the higher rates generally observed with EMG guidance are due to suboptimal positioning of the needle. Furthermore, if more toxin is used where injection takes place distal to the optimum location, the result may be an increase in antibody formation and reduced response to the toxin. It is also difficult to teach the effective use of EMG needle guidance where such descriptive interpretation is involved.

The need for improvement was confirmed during recent research of consensus needs of a group of clinicians ([name], 2016), which distilled specific needs relating to EMG needle guidance in this context. Four of these are particularly challenging and of interest for this study:

- 1) Isolating the EOM EMG signal by reducing contamination from other muscles;
- 2) Displaying the confidence that the needle is within the EOM;
- 3) Indicating the proximity of the needle to the EOM;
- 4) Providing a signal quality score.

Clinicians ranked the first two as higher priority than the third and fourth. Note that all are dependent upon learning more about the EMG signal characteristics that are affected by distance of the needle to the target muscle.

Despite the need, commercially available handheld EMG monitors of the type typically used to guide injections in this context do not appear to assist the clinician by isolating the extraocular EMG signal from interfering EMG signals, nor do they process the EMG signal to provide additional information such as confidence of location or proximity to the EOM. This presents a potential opportunity to develop the technology and deliver benefits to patients with improved treatment efficacy.

Considering this clear need for improvement, there is currently little evidence to support development of the EMG guidance technology used to treat strabismus with BTX. Detailed analysis of extraocular muscle EMG obtained using a monopolar needle electrode is needed to identify feasible approaches in improving EMG needle guidance.

This pilot study is an exciting opportunity to gain more knowledge and explore the hypothesis that there is a relationship between characteristics of the EOM EMG signal and the proximity of the needle to the rectus muscle belly. This knowledge may then be used to develop a new needle guidance technology, potentially paving the way for far less subjective evaluation of the “rain on a tin roof” sound.

## 2 STUDY OBJECTIVES

The principal objective is to identify any signal characteristics that could potentially be indicative of the location of the EMG needle with respect to the target muscle.

A secondary objective is to indicate the value of developing the technology of EMG needle guidance in this application, and inform the design of any future research.

## 3 STUDY DESIGN

This is a cross-sectional observational study.

### 3.1 MATERIALS

The key equipment and software required are:

- EMG Signal Capture System, comprising:
  - A USB powered bio-signal acquisition device to capture the EMG signal;
  - A buffer device to allow the EMG signal to be detected;
  - A USB camera (webcam) to record audio and video of the procedure;
  - An office laptop to drive the signal acquisition device and camera;
  - Acquisition software to capture the EMG signal and event markers;
- R software environment for statistical computing and graphics.
- MATLAB software environment for data analysis and software development.

Further details of the EMG signal capture system, including specification analysis, are in APPENDIX 1: EMG SIGNAL CAPTURE SYSTEM.

Patient / procedure meta-data	
 
• Patient age
 
• Units of BTX injected
 
• The target muscle (lateral or medial, left or right)
 
• Any known contraindications to optimal EMG needle guidance, e.g. scar tissue around the target muscle
 
• Whether: 
 
○ The patient is repeat or 'routine', where no follow-up is planned and the patient has been seen at least once before for the same treatment; or
 
○ The patient is 'new', and has not previously received BTX for the treatment of strabismus by [name].
 
 
 
• Approximate distance between the centre of the reference skin electrode and the needle insertion point
 
• The outcome of the routine skin electrode impedance check
 
	To include potential characteristics for statistical analysis and help identify potential causes of outliers
Patient pre-	Typically measured in units of prism dioptres	To allow comparison of signal

treatment angle of deviation		characteristics with the amount of improvement in deviation, and help evaluate signal processing and statistical analysis outcomes
-------------------------------------	--	--

There will also be follow-up for each patient, within four weeks, but typically around two to three weeks following treatment. This is current practice for new patients and is an additional requirement for repeat patients. The data recorded during the follow-up is:

Data	Detail	Justification
Patient post-treatment angle of deviation	Typically measured in units of prism dioptres	To allow comparison of signal characteristics with the amount of improvement in deviation, and help evaluate signal processing and statistical analysis outcomes

Once the data has been captured, processing and statistical pattern recognition of the recorded data will address the study objectives.

Duration: up to 20 weeks. [name] clinic takes place every two weeks and each list includes approximately seven patients. If five successful recordings are made per clinic, 25 recordings will be made over a period of 10 weeks; allowing an additional four weeks for follow-up and four weeks contingency equates to 20 weeks. Data processing and analysis will take place once the study has ended. See Section 9.2 for a Gantt chart.

Subjects: Signals will be recorded from 25 adult patients receiving treatment for strabismus with EMG guided injection of BTX.

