#### 8.14 RISKS TO COMPLETION OF STUDY

Impact	High	Sponsorship cannot be agreed		
	Medium	EMG Capture System is not suitable for the intended environment	Patients are not recruited at anticipated rate due to lower than expected throughput of clinic, or fewer patients consent to recording of data	
	Low			
		Low	Medium	High
		Probability		

Mitigating actions are:

- Sponsorship cannot be agreed: sponsorship to be sought at earliest opportunity from Royal Liverpool Hospital.
- Patients are not recruited at anticipated rate: three week contingency included in time scales.
- EMG Capture System is not suitable for the intended environment: the system will be tested in the intended environment before the first patient is recruited to identify any use or environmental issues.

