## 10 END OF STUDY

The study will formally end when the follow-up has been completed for the last participant. At the end of the study, a Project Evaluation will be carried out, as discussed in Section 8.13.

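### Does it matter that the study duration in section 3.2 adds up to 18 weeks rather than 20, with a different contingency in section 8.14?

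*Combined protocol and SAP*

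**What the plan says.** Section 3.2 (Duration) starts from the clinic timetable: the "clinic takes place every two weeks and each list includes approximately seven patients". It continues: "If five successful recordings are made per clinic, 25 recordings will be made over a period of 10 weeks". It then adds the remaining parts, "allowing an additional four weeks for follow-up and four weeks contingency equates to 20 weeks". The follow-up allowance matches the data-collection text of the same section: "There will also be follow-up for each patient, within four weeks". The study summary also gives 20 weeks, worded as a maximum.

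Section 8.14 rates slow recruitment as medium probability and medium impact, and answers it with one line: "Patients are not recruited at anticipated rate: three week contingency included in time scales".

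Section 9.2 puts the start of recruitment at 10/01/2019 and the last follow-up at 17/04/2019.

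On numbers, section 3.2 (Subjects) says "Signals will be recorded from 25 adult patients receiving treatment for strabismus", and section 7 describes 25 as the sample size expected. Section 10 says "The study will formally end when the follow-up has been completed for the last participant".

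**The concern.** The sum in section 3.2 is wrong as printed, and the contingency differs between two sections of the same version. That contingency is the only mitigation section 8.14 lists for slow recruitment, so the protocol appears not to know the size of its one buffer. The milestones in section 9.2 span about 14 weeks and match neither total.

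Section 10 ties the end of the study to the last participant without saying what makes a participant the last. Other things hang on that end: analysis begins after it (section 3.2), identifiable data are destroyed within three months of it (section 8.4), and section 8.11 treats a premature end differently from a planned one. If recruitment ran slowly, a few disputed weeks might decide whether 25 is reached, and section 7 ties the number of model parameters to the sample size.

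**Working it through.** **Inputs.** Target 25, five recordings per clinic, one clinic every two weeks, follow-up within four weeks, contingency four weeks (all section 3.2); contingency three weeks (section 8.14); ceiling 20 weeks (summary and section 3.2); dates 10/01/2019 and 17/04/2019 (section 9.2).

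**Step 1: the recording period.** 25 / 5 = 5 clinics; 5 × 2 = 10 weeks. The plan's figure is reproduced.

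**Step 2: the total.** Total = recording + follow-up + contingency.
- Section 3.2 contingency: 10 + 4 + 4 = 18.
- Section 8.14 contingency: 10 + 4 + 3 = 17.
- Recording counted only from first to fifth clinic (8 weeks): 8 + 4 + 4 = 16, or 8 + 4 + 3 = 15.

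None gives 20, so the stated total is not reproduced. Reaching it would take 20 − 10 − 4 = 6 weeks of contingency, a figure that appears nowhere in the plan.

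**Step 3: the milestones.** 10/01/2019 to 17/04/2019 is 97 days, or 97 / 7 = 13.9 weeks. Two readings come within a day of this: 10 + 4 = 14 weeks (98 days) with no contingency, and 8 + 3 + 3 = 14 weeks with the typical three-week follow-up and the three-week contingency. The dates therefore do not settle which contingency was meant.

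**Step 4: does the discrepancy affect reaching 25?** Count the clinics that still leave four weeks for follow-up. Convention A puts the first clinic at day 0 and the others at 14-day steps, with the last at least 28 days before the limit. Convention B follows section 3.2 and charges two weeks per clinic: (weeks − 4) / 2, rounded down.

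| Length | Clinics, A | Needed per clinic, A | Clinics, B | Needed per clinic, B |
|---|---|---|---|---|
| 20 weeks | 9 | 25/9 = 2.8 | 8 | 25/8 = 3.1 |
| 18 weeks | 8 | 25/8 = 3.1 | 7 | 25/7 = 3.6 |
| 17 weeks | 7 | 25/7 = 3.6 | 6 | 25/6 = 4.2 |

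Every required rate is below the planned five, from lists of about seven.

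**Step 5: a slow-recruitment case.** Take three recordings per clinic, an assumed rate that is not in the plan. The 20-week ceiling gives 9 × 3 = 27 (A) or 8 × 3 = 24 (B). Section 7 allows one parameter per ten subjects: 24 / 10 = 2.4, so still two parameters. A limit of 17 weeks under convention B would give 6 × 3 = 18 and only one parameter (18 / 10 = 1.8), but nothing in the plan makes 17 weeks a limit.

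**The case for a change.** The best case for a change is that the errors are plain, cheap to correct and attached to the only stated defence against a recognised risk. The arithmetic part of that stands: 18 is not 20, and three is not four. It is also true that at an assumed three recordings per clinic the yield could fall on either side of 25 depending on which total governs.

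The rest is weaker. The plan states only one limit, 20 weeks, in two places, so there is no real contest between totals. A target of 25 set beside a maximum duration is readily understood as stopping at whichever is met first, and section 7's description of 25 as expected fits that. Section 10's end point is known once the last follow-up has taken place, whatever the final count, so the analysis start and the data-destruction clock are both fixed. Section 8.11 has a line for a premature end, and the Principal Investigator it would consult is the ophthalmologist who takes consent before the procedure (section 8.3).

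Nor do the documents point to a correction. Setting the contingency at six weeks would make the sum work, but that number is obtained only by working back from 20. It would double the figure in section 8.14, and would count contingency twice if 17/04/2019 already contains some. The slip could equally lie in the total.

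**Conclusion.** The concern is factually right and inconsequential. Section 3.2 overstates its own sum by two weeks, and the contingency differs by one week between sections 3.2 and 8.14. This is a clerical planning slip. At the planned rate 25 recordings are reached under 17, 18 or 20 weeks, and each of those lengths respects the 20-week ceiling. The outcome measures, follow-up window and models do not depend on which figure was intended. The missing recruitment-end sentence is a detail that the study team can supply from the target and the ceiling already given.

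This rests on three assumptions: the first clinic falls on 10/01/2019 for the day-based count, clinics stay fortnightly, and each patient is allowed the full four weeks of follow-up. The Gantt chart cited in section 3.2 could not be seen, and the text available between sections 3.2 and 3.4 was incomplete. The remark about a missing recruitment-end rule is therefore limited to the text that could be read; the two arithmetic points do not depend on it. Making the figures agree would be ordinary editing if the protocol is reissued for another reason, and would alter nothing that the study does or concludes.

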### **3.4 PERSONNEL**

The procedure being observed will be carried out by [name]. There are no training needs identified for this protocol.

Pre-treatment and post-treatment angle of deviation measurements and other patient data as required by the Method will be provided by an orthoptist. There are no training needs identified for this protocol.

The data recording will be carried out by [name]. There are no training needs identified for this protocol.

Data analysis will be carried out by [name]. There are no training needs identified for this protocol.

### **3.5 STUDY OUTCOME MEASURES**

#### **3.5.1 Primary**

- The change in the EMG signal as the needle approaches, and enters, the target extraocular muscle.

#### **3.5.2 Secondary**

- Clinician's score of the step change from baseline EMG to 'active' EMG level heard immediately prior to delivery of BTX;
- Clinician's score of their confidence in accurate needle placement;
- Clinician's score of overall quality of the EMG signal heard during the procedure;
- Change in patient's angle of deviation following treatment.

## **4 PARTICIPANT ENTRY**

### **4.1 PRE-REGISTRATION EVALUATIONS**

None, since this is an observational study.

